5.1.1.2. Inhibitor Subgroups

Selected tables will further be presented by the following groups:

- Patients in the inhibitor subgroup (see Section 5.1.2.5)
- Patients not in the inhibitor subgroup

For longitudinal data, the safety or efficacy periods included for these groups is the entire period, again as described in Section 5.4.

Patients in the inhibitor subgroup will be further split by the sub-classification of inhibitor as described in Section 5.1.2.5, namely:

- Patients with high-titer inhibitors
- Patients with low-titer inhibitors that meet the clinically meaningful criteria as defined in Section 5.1.2.5
- Patients with low-titer inhibitors that do not meet the clinically meaningful criteria

For this presentation, the analysis of longitudinal data will be presented for the entire safety or efficacy periods, dichotomized as described in Section 5.4.7, i.e.:

- From start of the relevant period up to the date of the positive inhibitor (all patients in the inhibitor subgroup combined)
- From date of positive inhibitor to the end of the relevant period

The definition of a positive inhibitor and the date of onset are described in Section 5.1.2.4.

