5.1.2.5. Subgroup Definitions

Surgery Subgroup

The Surgery Subgroup is defined as all patients who have undergone major surgery after first dose of study drug. This set will be described in the disposition table and all analyses and listings of major surgeries will be presented for this population.

Inhibitor Subgroup

Patients developing a positive inhibitor after exposure to rFVIII Fc will be included in Inhibitor Subgroup. Within this subgroup, there are several further classifications:

1. Patients with high-titer inhibitors, defined as in Section 5.1.2.4
2. Patients with low-titer inhibitors, defined as Section 5.1.2.4, that meet the below clinically meaningful criteria
3. Patients with low-titer inhibitors that do not meet the below clinically meaningful criteria

The delineation of clinically meaningful will be performed on a case-by-case basis via medical adjudication just prior to the interim or final analyses, based upon the data available for the analysis. This assessment will take account of relevant clinical factors, including but not limited to:

- Entry to the ITI sub-study
- Any bypassing or immunomodulatory agents received up to 4 weeks before inhibitor development and any time after
- Withdrawal from the study due to complications assessed as related to inhibitor development
- Any SAE of a bleeding event up to 4 weeks before inhibitor development or any time after

- A pattern of non-serious treated bleeding events which require a change in study drug (rFVIII Fc) regimen

Patients who undergo ITI will be part of the ITI Analysis Set (see Section 4.4). By definition, all high-titer inhibitors are clinically meaningful, as patients with high-titer inhibitors must either enter the ITI sub-study or withdraw.

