Summary of prophylactic and ITI compliance
Summary of EPD entry compliance by treatment regimen
Efficacy
Summary of bleeding episodes by treatment regimen
Summary of bleeding episodes by inhibitor subgroup
Summary of bleeding episodes by inhibitor sub-classification
Summary of annualized bleeding rates by treatment regimen
Summary of annualized bleeding rates by inhibitor subgroup
Summary of annualized bleeding rates by inhibitor sub-classification
Summary of annualized bleeding rate by type of bleed and treatment regimen
Summary of annualized bleeding rates by type of bleed and inhibitor subgroup
Summary of annualized bleeding rates by type of bleed and inhibitor sub-classification
Summary of annualized bleeding rate by location of bleed and treatment regimen
Summary of annualized bleeding rates by location of bleed and inhibitor subgroup
Summary of annualized bleeding rates by location of bleed and inhibitor sub-classification
Summary of annualized bleeding rate by location, type of bleed and treatment regimen
Summary of annualized bleeding rates by location, type of bleed and inhibitor subgroup
Summary of annualized bleeding rates by location, type of bleed and inhibitor sub-classification
Summary of annualized bleeding rate by history of bleeding (estimated frequency of bleeds in prior 3 months) by treatment regimen
Summary of annualized bleeding rate - patients with no major protocol deviations potentially impacting efficacy by treatment regimen
Summary of patient's assessment of response to rFVIII Fc injections for the treatment of bleeding episodes by treatment regimen
Summary of patient's assessment of response to rFVIII Fc injections for the treatment of bleeding episodes by compliance to treat the bleed and treatment regimen
Summary of number of injections required for resolution of a bleeding episode by treatment regimen
Summary of number of injections required for resolution of a bleeding episode by inhibitor subgroup
Summary of number of injections required for resolution of a bleeding episode by inhibitor sub-classification
Summary of dose (IU/kg) of rFVIII Fc for resolution of bleeds by treatment regimen
Summary of dose (IU/kg) of rFVIII Fc for resolution of bleeds by inhibitor subgroup
Summary of dose (IU/kg) of rFVIII Fc for resolution of bleeds by inhibitor sub-classification
Summary of physician's global assessment of the response for episodic and prophylactic regimens

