Summary of physician's global assessment of the response for ITI regimens
Summary of health outcomes for episodic and prophylactic regimens
Summary of incremental recovery (IR) (IU/dL per IU/kg) for episodic and prophylactic regimens
ITI

	Statistical Analysis Plan	Final v1.0
---	----------------------------------	-------------------

Summary of ITI response and relapse
Surgery
Investigators'/surgeons' assessment of patients' hemostatic response to rFVIIIFc post surgery
Number of injections and dose required to maintain hemostasis during major surgery
Estimated total blood loss during major surgery
Total rFVIIIFc consumption (IU/kg) per major surgery
Summary of number of bleeds after surgery per major surgery
Adverse events
Overall summary of rFVIIIFc treatment-emergent adverse events by treatment regimen
Overall summary of rFVIIIFc treatment-emergent adverse events by inhibitor subgroup
Overall summary of rFVIIIFc treatment-emergent adverse events by inhibitor sub-classification
Overall summary of rFVIIIFc treatment-emergent adverse events by treatment regimen and EPD entry compliance
Summary of rFVIIIFc treatment-emergent adverse events by treatment regimen
Summary of rFVIIIFc treatment-emergent adverse events by inhibitor subgroup
Summary of rFVIIIFc treatment-emergent adverse events by inhibitor sub-classification
Summary of rFVIIIFc treatment-emergent adverse events by treatment regimen and EPD entry compliance
Summary of rFVIIIFc treatment-emergent adverse events by treatment regimen and preferred term in descending order of incidence
Summary of rFVIIIFc treatment-emergent serious adverse events by treatment regimen
Summary of rFVIIIFc treatment-emergent adverse events by severity and treatment regimen
Summary of rFVIIIFc treatment-emergent adverse events by relationship to treatment and treatment regimen
Summary of severe rFVIIIFc treatment-emergent adverse events by treatment regimen and preferred term in descending order of incidence
Summary of rFVIIIFc treatment-emergent adverse events leading to treatment discontinuation or withdrawal by treatment regimen
Routine laboratory
Summary of laboratory results and change from baseline for episodic and prophylactic regimens: Hematology
Summary of laboratory results and change from baseline for ITI regimen: Hematology
Shifts from baseline to minimum/maximum post-baseline value for laboratory results: Hematology

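### The two low-titer inhibitor classes are defined partly by outcomes that are then tabulated for them, so differences between their columns are partly built in and the tables need a pooled low-titer column and a footnote

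*SAP*

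**What the plan says.** SAP 5.1.1.2 (Inhibitor Subgroups) divides patients with an inhibitor into three groups: high titer, "Patients with low-titer inhibitors that meet the clinically meaningful criteria as defined in Section 5.1.2.5", and low titer not meeting those criteria. Longitudinal data are shown before and after the date of the positive inhibitor. The period before pools all inhibitor patients; the period after runs to the end of the safety or efficacy period.

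SAP 5.1.2.5 decides the low-titer class on a "case-by-case basis via medical adjudication just prior to the interim or final analyses", from the data then available. The factors are stated to be non-exhaustive. They include ITI entry, bypassing or immunomodulatory agents (from 4 weeks before the inhibitor onward), and three others:

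- for serious bleeding, with an open-ended window: "Any SAE of a bleeding event up to 4 weeks before inhibitor development or any time after"
- for leaving the study, limited to one kind of reason: "Withdrawal from the study due to complications assessed as related to inhibitor development"
- for other bleeding, with no count or window given: "A pattern of non-serious treated bleeding events which require a change in study drug (rFVIII Fc) regimen"

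SAP 6.1, 7.4.2 to 7.4.4, 7.4.7, 9.3.2 and 9.3.3 present disposition, bleeding episodes, ABR, consumption and TEAEs by these groups. The list of tables in SAP 12 confirms it, for example "Summary of annualized bleeding rates by inhibitor sub-classification" and the summaries of "treatment-emergent adverse events by inhibitor sub-classification". SAP 5.1.1 gives efficacy tables no overall column by default, and no section adds a pooled low-titer column, a landmark or a caveat.

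**The concern.** A child with a low-titer inhibitor who has a serious bleed, or withdraws because of the inhibitor, is likely to be placed in the clinically meaningful class for that reason. The tables then report serious bleeds and withdrawals by class. The not-meaningful column looks mild partly because children with those events were moved out of it.

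At stake is how the study's evidence on low-titer inhibitors is read. Two adjacent columns, one mild and one not, invite the conclusion that some low-titer inhibitors are benign. Columns defined by their own outcomes cannot support that. The pre-inhibitor data, which are largely free of this sorting, are pooled over all inhibitor patients, so a reader cannot see whether the classes already differed before onset.

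**Working it through.** The plan states no figure on this point, so there is none to reproduce. The check has two parts.

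**1. Sorting factors against tabulated outcomes**

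| Factor in SAP 5.1.2.5 | Where it reappears by class | Overlap |
|---|---|---|
| Bleeding SAE | Preferred terms, SAP 9.3.3 | Strong. Bleeds are AEs only if serious (protocol 15.1.1, SAP 9.3), so bleeding terms there come mainly from the events used to sort |
| Inhibitor-related withdrawal | Disposition by reason, SAP 6.1; discontinuation rows, SAP 9.3.2 | Strong for that reason, partial overall, since disposition counts every withdrawal |
| Treated bleeds that change the regimen | Bleeding episodes and ABR, SAP 7.4.2 to 7.4.4 | Direct in kind; no count or window is given |
| ITI entry | Consumption, SAP 7.4.7; ABR through follow-up time | Indirect. Protocol 10.2.5.2.1 ties ITI eligibility at low titer to uncontrolled bleeding or need for bypassing agents |
| Bypassing or immunomodulatory agents | Not itself one of these outcomes | Indirect, through bleeding |

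The windows also largely coincide. The bleeding-SAE and agent windows start 4 weeks before the inhibitor and stay open; the outcome window starts at the inhibitor and runs to the end of the period.

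**2. Illustration of size (all inputs assumed)**

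Suppose all low-titer children have the same true rate of 4 bleeds per year, one year of follow-up after the inhibitor, and 5% of bleeds serious. A child is classed as meaningful with at least 1 serious bleed or at least 6 bleeds. The threshold of 6 is invented, as the SAP has none. Serious bleeds S are Poisson(0.2) and non-serious bleeds M are Poisson(3.8). A child is not meaningful if S = 0 and M ≤ 5.

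- P(not meaningful) = e^(−0.2) × P(M ≤ 5) = 0.8187 × 0.8156 = 0.668, so P(meaningful) = 0.332.
- Mean ABR, not meaningful = 3.8 × P(M ≤ 4)/P(M ≤ 5) = 3.8 × 0.6678/0.8156 = 3.11.
- Mean ABR, meaningful = (4 − 0.668 × 3.11)/0.332 = 5.8.
- Ratio 5.8/3.11 = 1.9, with no true difference.
- Bleeding SAE: (1 − 0.8187)/0.332 = 55% against 0%.

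Over true ABR 2 to 6, 3 to 10% serious, and a count threshold of 4, 6 or none, the ratio runs from 1.19 to 2.70. A second set of assumptions used ABR 1, 2 or 4, thresholds of 2 to 4 bleeds, follow-up of 0.25 to 1 or 0.5 to 2 years, 10% of bleeds serious and 10% withdrawn. It gives 1.8 to 4.3 if adjudication follows the rule exactly, and 1.25 to 2.55 if it has sensitivity 0.8 and specificity 0.9. The open window also favours longer-followed children for the meaningful class: mean follow-up 1.39 against 1.08 years in one case (ABR 2, threshold 3, follow-up 0.5 to 2 years).

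**Adding ITI time.** Under SAP 5.2.2 and 5.4.2, time on ITI counts in the efficacy period, and ITI can last 33 months (2.75 years). Give x extra years on ITI, at a fraction r of the original rate, to the meaningful class. The mean ABR is then (5.785 + 4rx)/(1 + x), where 5.785 is the 5.8 above with more digits.

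- All on ITI, x = 2.75, r = 0.25: (5.785 + 2.75)/3.75 = 2.28; ratio to 3.11 = 0.7.
- All on ITI, x = 1, r = 0.25: (5.785 + 1)/2 = 3.39; ratio 1.1.
- Half on ITI, x = 1, r = 1: (5.785 + 4.89)/2 = 5.34; ratio 1.7.

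So the built-in ABR contrast can shrink, vanish or reverse.

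**Control.** If the class is fixed by bleeding in the first 12 weeks and ABR is counted only afterwards, identical children give a ratio of 0.99 to 1.00. The artefact comes from overlapping the two windows.

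**The case against.** The case against making much of this is substantial, and most of it limits the size of the point.

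- *Adjudication is a medical judgement, not a rule.* True. The list is open and a bleeding pattern counts only if it changes the regimen. The judgement is still guided by these outcomes, and the contrast survives imperfect adjudication in the illustration without ITI time.
- *The meaningful column must show a higher ABR.* A reader might infer this. The documents do not support it, because ITI time is included and can pull that column's ABR down.
- *The tables will show an SAE contrast such as 55% against 0%.* A reader might infer this too. No planned row shows it. Protocol 15.3.2 makes inhibitor development itself a reportable SAE, so the any-SAE row in SAP 9.3.2 should be near 100% in every class. The stand-alone SAE table in SAP 12 is by treatment regimen only. A bleeding contrast would surface only in the preferred terms of SAP 9.3.3.
- *Consumption is not a sorting factor.* Correct. It is linked only through ITI entry and regimen changes.
- *The study is descriptive, and no comparison of the two classes is planned.* Correct. The harm is to interpretation. But descriptive tables are the evidence this study will offer on low-titer patients, and the plan attaches no caution to them.
- *Deleting the by-class columns would hide the results of an open-label adjudication.* A fair point, and the reason to keep them alongside a pooled column.

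**Conclusion.** The overlap is plain from the SAP. Differences between the two low-titer columns are partly produced by the classification and cannot show that some low-titer inhibitors are benign. The effect is clearest for bleeding-related preferred terms and inhibitor-related withdrawals. For ABR neither size nor direction can be fixed: the ratios above rest on assumed bleeding rates, thresholds, adjudication accuracy and ITI time, and are illustrative only.

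A reader might also infer that the main safety result is affected. It is not: the primary analysis in SAP 9.4.3.2 counts any confirmed inhibitor and does not use the split. This is a worthwhile, inexpensive improvement to presentation and interpretation.

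**What to change.** In SAP 5.1.1.2:

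- Add an all-low-titer column to the post-inhibitor disposition, bleeding, ABR, consumption and TEAE tables, and make high titer against all low titer the main display.
- Footnote the two low-titer sub-columns: the classes are defined partly by post-inhibitor bleeding, SAEs, withdrawal and ITI entry, and should not be compared on those outcomes.

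Keep the clinically meaningful split in the incidence analyses of SAP 9.4.3.3, where class membership is the outcome being counted. State that the listing of inhibitor patients shows each patient's class; SAP 12 names that listing without giving its content.

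Titer class is not wholly fixed at onset, since SAP 5.1.2.4 allows reclassification using later titers, dose and ITI start. It is not assigned from bleeding, SAEs or withdrawal, so it largely avoids the problem described here.

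The cost is one extra column and a footnote, with no new data.

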#### 7.3.2. Treatment

Enrolled subjects will report to the study site for 2 kinds of required visits during the Treatment Period:

- Scheduled Interim Visits: every 12 ( $\pm 2$ ) weeks by calendar date (Section 4.2.2.1). Subjects who develop high titer inhibitors will switch to a schedule of ITI Induction

CONFIDENTIAL

The information contained herein may not be used, disclosed, or published without the written consent of Bioerativ Therapeutics Inc.

Visits (Section 4.2.2.3 and, if applicable, Section 4.2.2.4) and, if they subsequently meet ITI complete success criteria within 33 months, will receive a tapering regimen and participate in Post-ITI Success Visits (Section 4.2.2.5).

- ED Milestone Visits: at 5 ( $\pm$ 1) EDs, 10 to 15 EDs, 20 to 25 EDs, and 50 to 55 EDs (Section 4.2.2.2).

In addition, telephone calls with the subject's parents/caregivers are planned approximately once a month. (Section 10.2.4.1.4).

Subjects who develop inhibitors may be eligible for 33 months of Immune Tolerance Induction Therapy (ITI), followed by a tapering off regimen of 3 months and follow up monitoring for 9 months (for a total of 12 months of monitoring post-ITI success) (Section 10.2.7, Section 4.2.2.4 and Section 4.2.2.5).

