5.4.2. Efficacy Period

The efficacy period will be used for the evaluation of efficacy and health outcome endpoints. For a patient to have an evaluable efficacy period over the duration of study, he must have at least 1 day of treatment for an episodic regimen or at least 2 prophylactic injections for prophylactic regimens.

The start and end, and the total duration of the efficacy period for a given treatment regimen is the same as the start and end, and the total duration of that treatment regimen defined in Section 5.2.4 with the exceptions described in the following two subsections. The start of the efficacy period for each patient is the start of their first treatment regimen and the end is the end of their last.

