5.4.4. Safety Period

The overall safety period is defined as beginning at the first dose of study medication rFVIII Fc. For patients who are subsequently enrolled, the safety period ends on the date of the Final Safety Follow-up Visit (by telephone or in person), 7 to 14 days after the last dose of rFVIII Fc. For patients who fail screening, this period ends on the date that this is confirmed.

The safety period on a specific treatment regimen is as described in Section 5.2 except that the end of the patient's last treatment regimen is the end of their safety period.

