5.4.7. Inhibitor Period

For patients who develop inhibitors, safety and efficacy data analysis will be dichotomized into periods before and after this event. The date of the inhibitor, that is, the date of the first sample with a positive test result (subsequently confirmed, see Section 5.1.2.4) will be leveraged for this purpose. The start and end of the inhibitor period are the start and end the relevant period, as defined in Sections 5.4.2 and Section 5.4.4.

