9.4.3.4. Additional Analyses

Patients with low titer inhibitors who remain in the main study may achieve remission without ITI. This is defined as negative inhibitor titers (< 0.60 BU/mL) in 2 consecutive determinations at least 28 days apart. These patients will be listed separately.

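### The post-onset part of the inhibitor sub-classification tables stays open after remission or ITI complete success, so annualized consumption, and possibly ABR, averages inhibitor and tolerised time

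*SAP*

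**What the plan says.** For patients who develop an inhibitor, SAP 5.4.7 states that "safety and efficacy data analysis will be dichotomized into periods before and after this event", the event being the first positive sample that is later confirmed. In the tables by inhibitor sub-classification, SAP 5.1.1.2 gives the second part as "From date of positive inhibitor to the end of the relevant period". SAP 5.4.7 adds that "The start and end of the inhibitor period are the start and end the relevant period". The outer limits come from SAP 5.4.2, where the efficacy period starts at "the start of their first treatment regimen and the end is the end of their last", and from SAP 5.4.4, where "the safety period ends on the date of the Final Safety Follow-up Visit".

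The SAP also defines two later changes of state. Remission without ITI (9.4.3.4) is "negative inhibitor titers (< 0.60 BU/mL) in 2 consecutive determinations at least 28 days apart", and it is used only for a listing. ITI complete success (7.4.9) requires negative titers, recovered IR and a half-life of at least 6 hours. It leads to tapering and relapse monitoring, and Protocol 7.3.2 describes ITI as "followed by a tapering off regimen of 3 months and follow up monitoring for 9 months".

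SAP section 12 plans sub-classification tables for bleeding episodes, ABR, consumption, injections and dose to resolve a bleed, and TEAEs.

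**The concern.** A patient whose inhibitor has cleared goes on contributing days, doses, bleeds and events to the post-onset part. For annualized measures those days enter the denominator. A child who reaches tolerance quickly contributes mostly time after tolerance, while a slow responder contributes mostly ITI time. A lower post-onset consumption or ABR could then reflect how follow-up is made up and not the burden of the inhibitor. Consumption and ABR are secondary endpoints, and describing experience with ITI is a secondary objective, so readers will use these rows.

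**Working it through.** **Inputs from the documents**
- Tapering 3 months and monitoring 9 months (Protocol 7.3.2).
- ITI dose 200 IU/kg/day, for up to 33 months (SAP 3.1.2.3).
- Follow-up prophylaxis 25 to 65 IU/kg every 3 to 5 days, with doses up to 80 IU/kg or more frequent dosing as required (Protocol 10.2.7.5). Costed here from 25 IU/kg every 5 days to 80 IU/kg every 3 days.
- Consumption and ABR are totals divided by efficacy-period days, times 365.25 (SAP 6.6.1.4, 7.4.3).

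**Assumed:** T, the months from onset to complete success, because the documents give no time to success. All time before success is costed at the ITI dose. Tapering doses are redacted and are costed as prophylaxis.

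**The plan's own figure:** 3 + 9 = 12 months after success, which matches the total in Protocol 7.3.2.

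**Earliest plausible T.** The first half-life test falls 12 weeks after IR is confirmed (Protocol 4.2.2.3), and confirmation needs two determinations at least a month apart (Protocol 10.2.7.4.2). With IR visits from ITI Week 4, that is about 4 + 4 + 12 = 20 weeks. The illustration therefore starts at T = 6 months.

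**Share of post-onset time after success:** 12/(T + 12).

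**Annual rates:** ITI 200 x 365.25 = 73,050 IU/kg. Prophylaxis from 25/5 x 365.25 = 1,826 to 80/3 x 365.25 = 9,740 IU/kg.

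**Open-interval consumption:** (T x 73,050 + 12 x p)/(T + 12), with p from 1,826 to 9,740. At T = 6 the lower end is (6 x 73,050 + 12 x 1,826)/18 = 25,568.

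| T (months) | Share after success | Open-interval IU/kg/year | Below ITI rate |
|---|---|---|---|
| 6 | 67% | 25,568-30,843 | 58-65% |
| 12 | 50% | 37,438-41,395 | 43-49% |
| 21 | 36% | 47,150-50,028 | 32-35% |
| 33 | 27% | 54,057-56,167 | 23-26% |

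**ABR:** (T x a + 12 x b)/(T + 12), with a before and b after success, both assumed.

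| a, b | T = 6 | T = 33 |
|---|---|---|
| 8, 2 | 4.0 | 6.4 |
| 4, 2 | 2.7 | 3.5 |
| 4, 4 | 4.0 | 4.0 |
| 2, 4 | 3.3 | 2.5 |

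Dilution occurs only if b is below a.

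**AEs.** SAP 9.3.2 and 9.3.3 count patients, each once per term, with no time denominator. With assumed TEAE rates of 1 per year before success and 0.5 after, the percentage with at least one event at T = 6 is 1 - exp(-0.5) = 39% if the interval closes at success and 1 - exp(-1.0) = 63% if it stays open. Added time can only hold or raise the percentage.

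**Low-titer remission without ITI.** The documents give neither the time to remission nor the time that follows it, so no size can be computed.

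**The case against.** The strongest reply is that nothing is mislabelled. The SAP announces a split before and after onset, and Protocol 16.2.1 and 16.5 likewise leave the separately summarized data without an end point. A reader might infer that the SAP presents these rows as results while an inhibitor is present; it does not say so. This stands: the point is a limit on interpretation, not a contradiction.

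Second, ITI time is already shown alone. By-regimen tables count only time on each regimen (SAP 5.1.1.1), and the ITI regimen ends when tapering starts (SAP 5.2.3). This also stands, but only for the ITI column. Tapering and later time are pooled into the prophylactic column, and low-titer remission time is not separated in any planned table. The ITI period in SAP 5.4.8 does not help, since it runs until the patient completes or leaves the study.

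Third, a reader might infer that AE results are diluted too. They are not, because they are patient counts. The AE issue is attribution: events in tolerised time are counted as post-inhibitor.

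Fourth, 12 months is a ceiling. SAP 7.4.9 describes monitoring of up to 9 months after tapering, and end of study stops all ongoing patients (Protocol 7.5). What time is retained is nevertheless largely inhibitor-negative, because relapse requires withdrawal (Protocol 11).

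**Conclusion.** This is a worthwhile improvement to a descriptive analysis and not an error in the plan. For ITI complete successes, open-interval consumption is 58-65% below the ITI rate if success comes at 6 months and 23-26% below at 33 months. Those figures rest on an assumed time to success, a full 12 months of follow-up, ITI dosing throughout the time before success, and tapering costed at prophylaxis doses. If tapering doses are higher or follow-up is shorter, the dilution is smaller.

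A fall in ABR is conditional on less bleeding after tolerance, for which the documents give no figure. A reader might also infer that the main safety result is affected. It is not: inhibitor incidence (SAP 9.4.3.2) does not use these periods.

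**What to change.** In SAP 5.1.1.2 and 5.4.7, keep the onset split and divide the post-onset part in two:
- (a) from onset to remission or ITI complete success, or to the end of the period if neither occurs;
- (b) after remission or ITI complete success.

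Date remission at the first of the two consecutive negative titers in 9.4.3.4. Date ITI success when all 7.4.9 criteria are met. Add a note that in ITI patients (a) includes some titer-negative time, because the first half-life test comes 12 weeks after IR is confirmed. A later confirmed positive inhibitor after remission, or a confirmed relapse after ITI success, returns subsequent time to (a). The remission case needs its own wording because 7.4.9 defines relapse only after ITI complete success.

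Show person-years for each part and give exposure-adjusted AE rates beside the percentages. The same edit can clear up the last sentence of 5.4.7, which read literally makes the inhibitor period coincide with the whole efficacy or safety period.

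The cost is SAP wording and extra rows. The inhibitor, IR, half-life and dosing data are already collected. The downside is small cells in a descriptive table.
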